### 5.3. Secondary analyses

ANCOVA (and sensitivity analyses) described above will be repeated at each of the time-points illustrated in Figure 1 (weeks 0, 8, 16, 40), using the OLBI (total score; then separate domain scores), and using the WEMWBS as an outcome, controlling for baseline scores. Outcomes at 6-months follow-up (pooled for both groups) will be compared to outcomes at the baseline assessment, using paired-samples t-tests (or an appropriate non-parametric test depending on the distribution of the data).

We will carry out an exploratory analysis of sickness absence, by comparing the mean number of sickness absence days reported by all participants for the 6 months preceding the start of the study, and the mean sickness absence days reported during the 6-month follow-up period after both groups completed the intervention. This within-group comparison will be carried out using a paired-samples t-test (or an appropriate non-parametric test depending on the distribution of the data).

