Data analysis method	
 
1. Trial data will be summarised using a CONSORT diagram and analyses will be based on intention-to-treat principles.
 
2. Between-group comparisons will be conducted at the end of each phase using ANOVA.
 
3. The primary analyses will examine between-group differences in occupational burnout (OLBI) severity over time (after each of the 3 phases, post-baseline).
 
4. Secondary analyses will involve comparing between-group differences in each of the OLBI burnout dimensions (exhaustion, disengagement), and in measures of subjective well-being and personal goal attainment.
 
5. We will also quantify and report intervention completion / dropout rates, and self-reported days on sickness leave.
 

Study Period	24 months (18 months active study period, plus 6 months analyses and dissemination)

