#### 3.3. Hypotheses

- A) Exposure to the intervention will be associated with significantly lower mean burnout severity by comparison to a waitlist (delayed intervention) control group
- B) After the control group is exposed to the intervention, there will be no significant differences in mean burnout level between the two groups (immediate intervention group, delayed intervention group)
- C) Mean burnout severity for all participants at the end of the 6-month follow-up period will be significantly lower than baseline severity (prior to intervention), but not significantly different to end-of-treatment severity, indicating maintenance of gains

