### 4. Study design

This will be a pragmatic, stepped wedge, open-label, randomised controlled trial. Consenting NHS staff will be randomly assigned to two groups, by a research assistant using a computerized randomization algorithm (applying a simple 1:1 randomization schedule). The study will be carried out in four phases, which are illustrated in Figure 1.

Figure 1. Stepped wedge trial design

Participants in both groups will be asked to complete outcome measures during a pre-intervention baseline assessment (week 0). After the baseline assessment, only participants in group 1 will access an 8-week intervention (controlled phase). Next, group 2 will access the intervention during an 8-week period (full implementation phase). Finally, we will collect further outcome measures 6 months after both groups have completed the intervention (follow-up phase). The outcome measures will be completed continuously at each of the measurement points outlined in the above timeline (weeks 0, 8, 16, 40). All measures will be completed online using an industry-standard survey system (Qualtrics – which automatically sends email reminders to consenting participants), which will be managed by a research assistant.

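### Section 5.3 runs the baseline-adjusted ANCOVA at week 0, where no test exists, and carries the week-8 test to weeks 16 and 40 without saying that the contrast has become early versus delayed treatment

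*Protocol*

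**What the plan says.** Section 5.3 of the protocol states that the ANCOVA and its sensitivity analyses "will be repeated at each of the time-points illustrated in Figure 1 (weeks 0, 8, 16, 40"). This covers the OLBI total, the OLBI domain scores and then "using the WEMWBS as an outcome, controlling for baseline scores".

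Section 4 fixes the schedule. Both groups "complete outcome measures during a pre-intervention baseline assessment (week 0"). Group 1 is then treated in weeks 0 to 8, when "only participants in group 1 will access an 8-week intervention (controlled phase"). Group 2 waits and has its own eight weeks of treatment from week 8 to week 16. The last assessment, at week 40, is placed "6 months after both groups have completed the intervention".

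On which comparison is primary, section 5.2 bases the test of Hypothesis A on week 8, adjusted for baseline. Item 3 of the data analysis method in the synopsis says that the primary analyses examine "between-group differences in occupational burnout (OLBI) severity over time (after each of the 3 phases, post-baseline").

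Hypothesis B in section 3.3 predicts that, once the delayed group has had the intervention, "there will be no significant differences in mean burnout level between the two groups".

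**The concern.** The list in section 5.3 applies one model at four visits, and the model does not answer the same question at each of them.

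- **Week 0.** The model adjusts the baseline score for itself. An analyst who follows the text has nothing to report. One who departs from it must either drop the visit or run an unadjusted baseline test, and neither is what is written.
- **Week 8.** Group 1 is treated and Group 2 is not. This is the contrast that tests the intervention.
- **Weeks 16 and 40.** Both groups have been treated, eight weeks apart. The contrast now asks whether earlier treatment leaves people better or worse off than later treatment. The text carries the same test forward without marking the change.

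The last change matters for two reasons. The synopsis gives all three post-baseline comparisons primary status, so a reader cannot tell whether the main claim rests on one test or three, or that two of the three do not compare treated with untreated nurses. Hypothesis B also makes a non-significant difference the predicted outcome. With an interval as wide as this trial will have, that outcome is likely even if the groups differ to a modest degree, and it could be reported as equal benefit.

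**Working it through.** **Inputs from the protocol.** Baseline at week 0; Group 1 treated in weeks 0 to 8; Group 2 treated in weeks 8 to 16; last assessment at week 40 (section 4). 67 per group, 134 in total, 30% dropout, target 192 (section 5.1).

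**Assumptions, not in the protocol.** A moderate effect is taken as 0.5 SD, the test as two-sided, and the correlation of baseline with the later score as 0 to 0.5. Each outcome is adjusted for its own baseline score.

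**The plan's own figure.** 134 / 0.70 = 191.4, rounded up to 192, as stated. With 67 per group and a 0.5 SD difference, two-sided power is 81.9%, consistent with the stated 80%. Nothing below depends on disputing the sample size.

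**Week 0.** The model is y = b0 + b1·group + b2·baseline + error. At week 0, y is the baseline score, so b0 = 0, b1 = 0, b2 = 1 fits every observation exactly. The residual sum of squares is zero with or without the group term, so the F ratio for group is 0/0. A simulated fit with 134 people gave slope 1.000, group coefficient about -1 × 10⁻¹⁶ and residual sum of squares about 3 × 10⁻²⁹, which is zero to machine precision. The same holds for the OLBI total, both domains and WEMWBS. The sensitivity model with site as a random effect also has no variance left to partition.

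**Weeks since completing the intervention.**

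| Visit | Group 1 (visit − 8) | Group 2 (visit − 16) | Contrast |
|---|---|---|---|
| Week 8 | 0 | not yet treated | treated vs untreated |
| Week 16 | 8 | 0 | early vs delayed |
| Week 40 | 32 | 24 | early vs delayed |

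The gap is 8 weeks at both later visits. At week 40, Group 1 has been followed 32/24 = 1.33 times as long as Group 2.

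**What a non-significant later contrast could rule out.** The 95% half-width in SD units is 1.96 × √(2/n) × √(1 − r²), with n per group.

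- n = 67, r = 0: 1.96 × 0.1728 = 0.34 SD.
- n = 67, r = 0.5: 0.339 × 0.866 = 0.29 SD.

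If nobody were lost (192 / 2 = 96 per group), the figures would be 1.96 × √(2/96) = 0.28 SD and 0.283 × 0.866 = 0.24 to 0.25 SD.

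Power at 67 per group for a true early-versus-delayed difference of 0.2 SD is 21% (r = 0) to 26% (r = 0.5). Such a difference would therefore come out non-significant about 74% to 79% of the time.

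**The case against.** The strongest reply has four parts.

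*The week-0 entry is a slip.* The same string of weeks is the list of measurement points elsewhere in the protocol, and the synopsis shows that only post-baseline comparisons were meant. A model with no residual variance cannot mislead anyone. This stands as to weight, but the text still specifies an analysis that cannot be done and disagrees with the synopsis.

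*Comparing the arms after both are treated is deliberate.* Hypothesis B plans it and section 4 gives the schedule openly. This stands. A reader might infer that weeks 16 and 40 are invalid or no longer randomised comparisons. The documents do not support that: the arms are still those formed by randomisation, and section 5.3 does not claim that the later contrasts estimate the effect against no intervention. What remains is the unmarked change of question, the primary label in the synopsis and the use of non-significance in Hypothesis B.

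*The timing gap may be harmless.* A reader might infer that it distorts the later results by a known amount. If both arms gained 0.5 SD and the gain halved every 12, 24 or 52 weeks, timing alone would give 0.19, 0.10 or 0.05 SD at week 16, and about 0.05 SD or less at week 40. No document gives a half-life, and Hypothesis C expects gains to be maintained. The point does not rest on these figures.

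*The six-month label is fair.* Section 4 counts from when both groups have finished, which is correct for the later group. A reader might infer that follow-up is misreported, but the week numbers are disclosed. It is enough to state the two intervals.

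**Conclusion.** The point holds in this form.

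The week-0 ANCOVA is a definite error of specification for every outcome adjusted for its own baseline, and it conflicts with the scope in the synopsis. It has no effect on the trial's conclusions once removed.

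The week-16 and week-40 ANCOVAs are legitimate randomised comparisons of early with delayed treatment. The faults are that section 5.3 does not say so, that synopsis item 3 makes them primary against section 5.2, and that Hypothesis B takes a non-significant difference as its expected confirmation. With the planned 67 per group, a non-significant result would be compatible with differences of up to roughly 0.3 SD even if the estimate were zero (0.29 SD at an assumed correlation of 0.5, 0.34 SD unadjusted). It therefore cannot establish equal benefit.

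The primary week-8 analysis and the sample size are untouched. The matter should be corrected, but it does not threaten the main result.

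**What to change.** - **Section 5.3:** delete week 0 from the ANCOVA list and describe baseline scores by arm.
- **Section 5.3 and synopsis item 3:** state that the primary test, and the estimate of effect versus no intervention, are at week 8 only. This brings the synopsis into line with section 5.2.
- **Weeks 16 and 40:** keep the between-arm ANCOVAs as secondary analyses. Label them early-versus-delayed contrasts, give weeks since completion for each arm, and report estimates with 95% confidence intervals. Replacing them with within-arm changes would give up a randomised contrast and leave Hypothesis B without a test.
- **Hypothesis B:** reword it as an estimate of the early-versus-delayed difference with its interval, and state that non-significance will not be read as equal benefit.
- **Follow-up:** describe week 40 as 32 weeks after completion for Group 1 and 24 weeks for Group 2, including where the groups are pooled.

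The cost is wording only, with no new data, visits or participants. The one real loss is that Hypothesis B can no longer be declared confirmed by a non-significant p-value.

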### 5.2. Primary analysis

Trial data will be summarised using a CONSORT diagram and all analyses will be based on *intention-to-treat* principles. Missing data will be imputed using an expectation-maximization algorithm, prior to conducting formal analyses.

The primary hypothesis test (A) will be based on comparing mean outcome measures between groups at week 8, as shown in Figure 1. Mean OLBI scores will be compared between groups using analysis of covariance (ANCOVA), controlling for baseline severity.

Sensitivity analyses will be performed to assess the robustness of the main findings. This will involve repeating the comparison of means whilst controlling for any potential site-effects (systematic differences in burnout between NHS services), introducing a site variable as a random effect.

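### The pooled week 0 to week 40 test of Hypothesis C is uncontrolled and contains part of Group 2's untreated change, so it can describe change over time but cannot support gains from the intervention

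*Protocol*

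**What the plan says.** Section 3.3 of the protocol states Hypothesis C in two parts. The first is: "Mean burnout severity for all participants at the end of the 6-month follow-up period will be significantly lower than baseline severity (prior to intervention". The second adds: "but not significantly different to end-of-treatment severity, indicating maintenance of gains".

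Section 5.3 gives the test of the first part: "Outcomes at 6-months follow-up (pooled for both groups) will be compared to outcomes at the baseline assessment, using paired-samples t-tests", or a non-parametric equivalent. There is no comparison group and no term for the untreated period.

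Section 4 fixes the timing. Baseline is common to both groups: "Participants in both groups will be asked to complete outcome measures during a pre-intervention baseline assessment (week 0". In the first eight weeks, "only participants in group 1 will access an 8-week intervention (controlled phase". After that: "Next, group 2 will access the intervention during an 8-week period (full implementation phase". Measures are taken at the points "outlined in the above timeline (weeks 0, 8, 16, 40", so Group 2 has a week-8 measurement directly before its own intervention.

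The effect of the intervention is tested separately under Hypothesis A. Section 5.2 bases that test on "comparing mean outcome measures between groups at week 8", by ANCOVA adjusted for baseline.

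**The concern.** The trial observes burnout without the intervention only in Group 2, and only between weeks 0 and 8. The pooled paired test adds that untreated change to everything that happens later and compares the sum with zero. Zero is the right reference only if burnout would have stayed level from week 0 to week 40 without the intervention. Nothing in the protocol supports that assumption. Participants volunteer after the study is advertised to staff, so some may enrol when burnout is high and drift back. Workload may also differ between the season of week 0 and that of week 40.

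At stake is the durability conclusion. Section 2 of the protocol presents the trial as the first experimental test of this intervention in the NHS. A significant fall from week 0, together with no difference from end of treatment, would satisfy Hypothesis C and carry its wording about gains, whether or not the intervention had done anything. The error can also run the other way: if waitlisted nurses worsen before treatment, the pooled change understates a real gain.

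**Working it through.** The protocol states no power, effect size or drift for Hypothesis C, so there is no figure of its own to reproduce. The check has three steps.

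**1. What the pooled change contains**

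With 1:1 allocation (section 4), each group is about half of the pooled sample:

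pooled change = ½ × (Group 1, weeks 0–40) + ½ × (Group 2, weeks 0–8, untreated) + ½ × (Group 2, weeks 8–40)

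Half of Group 2's mean waitlist change therefore enters directly. For example, an untreated fall of 0.2 SD in Group 2 contributes ½ × 0.2 = 0.1 SD. Natural change also sits inside the other two terms, and no untreated group exists after week 8 to measure it.

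**2. How often drift alone gives a significant fall**

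Inputs from the protocol (section 5.1):
- alpha 0.05, taken as two-sided (2.5% in the direction of a fall)
- 134 participants after the expected 30% dropout
- 192 recruited, which is the number analysed if everyone is kept through imputation

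Assumed, because the protocol gives no values:
- no intervention effect
- the same drift in both groups, 0.2 SD by week 40
- equal SDs at both visits
- a week 0 to week 40 correlation r of 0.5 to 0.7

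In SD units, SE = √(2(1 − r)/n) and the noncentrality is 0.2/SE. The probability of a significant fall follows from the noncentral t distribution with n − 1 degrees of freedom.

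| n | r | SE | 0.2/SE | P(significant fall) |
|---|---|---|---|---|
| 134 | 0.5 | 0.0864 | 2.32 | 63% |
| 134 | 0.7 | 0.0669 | 2.99 | 84% |
| 192 | 0.5 | 0.0722 | 2.77 | 79% |
| 192 | 0.7 | 0.0559 | 3.58 | 95% |

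A smaller drift of 0.1 SD gives 21% to 32% at n = 134 and 28% to 43% at n = 192.

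**3. How much is removed by starting Group 2 at week 8**

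This uses the same assumptions, with r also applied to the week 8 to week 40 pair in Group 2. The answer depends on when the 0.2 SD drift occurs.

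- *All in weeks 0–8, then flat.* Group 1 still carries 0.2 SD and Group 2 carries none, so the pooled shift is 0.1 SD. False significance falls from 63–84% to 21–32% at n = 134, and from 79–95% to 28–43% at n = 192.
- *Linear to week 40.* Weeks 0–8 hold 8/40 × 0.2 = 0.04 SD, and half of that is 0.02 SD. The pooled shift is 0.18 SD, and false significance falls only from 63–95% to 54–89%.

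In neither case does the rate come near 2.5%. The main difficulty is that there is no concurrent control, and the choice of starting visit for Group 2 is only part of it.

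**The case against.** The strongest reply is that the plan is consistent with itself. Week 0 precedes treatment in both groups, section 4 defines it as the baseline, and the test in section 5.3 matches the first part of Hypothesis C as worded. Week 0 is also unaffected by knowledge of allocation, provided it is completed before the allocation e-mail. Group 2's week-8 score comes after its members know that they are waiting, in an open-label trial, and may be shifted by that. All of this stands. A reader might infer that week 0 is the wrong baseline for Group 2 and that week 8 should replace it. The documents do not support that, and step 3 shows that the replacement would not cure the problem.

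A reader might also infer that the waitlist data go unused. They do not: Group 2's week-8 score is the control arm of the primary ANCOVA. It is absent only from the test of Hypothesis C.

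A third tempting reading is to count only Group 2's share of the drift as error, as if Group 1 stayed level. With randomised groups and no intervention effect, regression to the mean and season act on both groups, so the coherent illustration is a common drift.

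Finally, the effect claim sits in Hypothesis A, and the first part of Hypothesis C says only that the mean will be lower. That is fair. But Hypothesis C goes on to speak of gains being maintained, and this wording goes further than an uncontrolled comparison can support. An analysis plan may add contrasts, but the reading is fixed in the protocol.

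**Conclusion.** The point holds in a limited form. The pooled week 0 to week 40 comparison is uncontrolled. It includes half of Group 2's mean untreated change, and Hypothesis C words the result as gains from treatment. Under the stated assumptions, a common drift of 0.2 SD makes the fall significant 63% to 95% of the time with no intervention effect, against 2.5% nominal in that direction. These rates illustrate sensitivity and do not predict the result: the protocol gives no OLBI SD, correlation or expected drift, and the drift could be upward, which would hide a gain.

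This is a matter of inference from one secondary analysis. It is not a contradiction in the plan, and the randomised week-8 primary test is untouched. The change should be made, because as written the plan can lead to a misleading conclusion about durability and the data needed to avoid this are already scheduled.

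**What to change.** - Reword Hypothesis C and section 5.3 so that the pooled week 0 to week 40 comparison describes change over time, and state that only the randomised week-8 contrast supports an effect of the intervention.
- Report Group 2's untreated change (weeks 0–8) beside its change over the treated period (weeks 8–16) and beside the pooled change to follow-up.
- For the second part of Hypothesis C, define end of treatment as week 8 for Group 1 and week 16 for Group 2. Note that week 40 is then 40 − 8 = 32 weeks after treatment in Group 1 and 40 − 16 = 24 weeks in Group 2.
- Add, as a sensitivity analysis and not a replacement, the follow-up comparison that starts Group 2 at week 8. State that it removes only part of any natural change and that the week-8 score was given with allocation known.

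The cost is protocol wording and a few more lines of analysis. No new measurement is needed. The price in interpretation is a more modest long-term claim.

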#### 3.2. Secondary Objectives

- To assess if the intervention improves subjective well-being
- To assess if the intervention improves personal goal attainment
- To assess if the intervention reduces sickness absence
- To quantify completion and dropout rates

[figure not shown]

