##### *Exclusion criteria*

- Currently accessing or referred to any concurrent psychological intervention delivered by a professional.
- Nurses that are currently not in active service at the time of recruitment (e.g., on sick leave, maternity leave or suspended for any reason).

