### *Secondary measures*

The Warwick-Edinburgh Mental Well-being Scale (WEMWBS) is a 14-item questionnaire; each answered on a 1 to 5 Likert scale. Items cover different aspects of eudaimonic and hedonic mental wellbeing and are worded positively. Item scores are summed to produce a total score (range: 14 to 70), where higher scores indicate greater psychological well-being. Psychometric testing has indicated that this measure was valid, reliable and acceptable measure of well-being in adult respondents (Tennant et al., 2007); with good internal consistency (Cronbach's alpha = .89 to .91) and test-retest reliability (.81).

Participants will be asked to report the number of sickness absence days they have had during the 6-month period preceding the start of the study, and will self-report any sickness absence days taken during the active study and observation period.

Participants will also be asked to report basic demographics (age, gender, ethnicity) and generic information about their work setting (adult services, children's services, inpatient vs. outpatient care).

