##### *Data collection and safeguarding procedures*

- All participants irrespective of group allocation will be asked to complete the primary and secondary measures described above, at four assessment points, as illustrated in Figure 1 (weeks 0, 8, 16, 40). The measures will be gathered by an independent researcher, who is not involved in the intervention. The researcher will use a secure, web-based, data collection system called Qualtrics.

Therefore, all data collection will be in electronic form, using unique participant pseudonyms, which cannot personally identify any of the study participants, or identify their random allocation.

- At the time of attendance at their initial group intervention session, participants will be asked to complete a brief checklist where they will report basic demographics and generic information about their role (see Appendix 3). These paper-based surveys will be entirely anonymous (no names, pseudonyms or identifiers), in order to protect participants' confidentiality. Participants will be asked to deposit their survey into a box, which will be managed by a member of the research team, who will then transcribe the results onto a spreadsheet, which will be safely stored in a secure network drive. The only reason to collect these data is to enable the research team to provide basic aggregated sample characteristics (e.g., mean age and standard deviation, % of people from a minority ethnic group, etc.) This will enable us to assess if the study sample is broadly representative of the wider NHS workforce or not.
- The dataset will be stored in a secure University network drive, only accessible to members of the research team, which is located behind The University of Sheffield Firewall. This will ensure the security and adequate storage of research data, consistent with NHS and academic codes of information governance and data protection.
- All analyses will be carried out at a University site, and data will be held in a restricted-access drive. The study dataset will be held at the University for a minimum of 5 years after the conclusion of the study.

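### The sickness-absence objective asks for an intervention effect, but the only planned analysis is a pooled before-after comparison that leaves the randomised weeks 0-8 unused and whose two windows may differ in length

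*Protocol*

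**What the plan says.** The protocol words the objective as a question about effect: "To assess if the intervention reduces sickness absence" (section 3.2; the Synopsis has the same aim for self-reported absence).

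Two kinds of absence data are planned under Secondary measures in section 4.3. One covers the past: "Participants will be asked to report the number of sickness absence days they have had during the 6-month period preceding the start of the study". The other is prospective: participants "will self-report any sickness absence days taken during the active study and observation period". Section 4.4 (Data collection and safeguarding procedures) has everyone, whatever their allocation, complete the primary and secondary measures "at four assessment points, as illustrated in Figure 1 (weeks 0, 8, 16, 40").

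Section 5.3 then fixes the analysis. It consists of "comparing the mean number of sickness absence days reported by all participants for the 6 months preceding the start of the study" with "the mean sickness absence days reported during the 6-month follow-up period after both groups completed the intervention". The test is a paired t-test or a non-parametric alternative. The section calls the analysis exploratory and describes it as within-group. The between-group ANCOVA in the same section names the OLBI and the WEMWBS, not absence.

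**The concern.** The question is causal and the analysis is not. By week 16 both arms have had the programme, so a pooled change from before the study to after it has no comparator. A fall or a rise could come from the intervention, a general trend in absence, the time of year, differences in recall, or the rule on who could enter. No result of the paired test tells these apart.

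The trial does have a controlled comparison for this outcome. During weeks 0-8 only group 1 has access to the intervention, and absence is to be reported in both arms. The protocol does not use it.

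The two windows, both described as six months, also do not have the same length on the protocol's own week schedule, and no rate or offset is stated. What is at stake is that a randomised trial reports a before-after change in absence, and readers take it for an intervention effect.

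**Working it through.** **Inputs from the protocol**
- Assessments: weeks 0, 8, 16 and 40 (sections 4 and 4.4).
- Group 1 has the intervention in weeks 0-8 and group 2 in weeks 8-16 (section 4).
- Pre-study window: six months (sections 4.3 and 5.3), taken here to end at week 0.
- Follow-up window: six months after both groups finish (section 5.3).
- Sample size: 134 analysed, 192 recruited (section 5.1).

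**1. Length of the follow-up window**
- By schedule: 40 − 16 = 24 weeks = 168 days.
- Six calendar months: 365.25 / 2 = 182.6 days = 26.1 weeks.
- The stated six months is therefore not reproduced from the week numbers. It would end at week 16 + 26.1 = 42.1.

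**2. Effect of unequal length, if days are counted from week 16 to week 40**
- With a constant absence rate the ratio of expected days is 168 / 182.6 = 0.920, a fall of 8.0% with no effect.
- With exactly 26 weeks: 1 − 24/26 = 7.7%. With six months of 181 to 184 days: 7.2% to 8.7%.
- The protocol gives no absence level. For an assumed 2, 5 or 8 days per six months the fall is 0.16, 0.40 or 0.64 days.

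**3. Effect on the paired test, under the same reading**
- Let b = 0.080 and r = 0.920. Assume SD/mean = c, equal in both windows, and correlation ρ between windows. The noncentrality is b√n / [c√(1 + r² − 2ρr)].
- Example with c = 1, ρ = 0.6, n = 134: 0.0801 × 11.58 / 0.862 = 1.08, which gives a probability of 0.187 of p < 0.05 with no effect.
- Over c from 1 to 3 and ρ from 0 to 0.6 (assumptions, not protocol figures), this probability runs from about 6% to 19% at n = 134 and from 6% to 25% at n = 192, against a nominal 5%. For widely spread data (c of 2 or 3) it is at most about 10%, so the mismatch shifts the estimate more than it inflates the error rate.

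**4. Other readings of the follow-up window**
- If the week-40 item asks about the past six calendar months, the window starts at week 40 − 26.1 = 13.9. The lengths match and the artefact in step 2 is zero, but 16 − 13.9 = 2.1 weeks of group 2's intervention lie inside the window.
- If week 40 is a rounded label and the survey really falls near week 42, lengths match with no overlap.
- The document does not give the recall wording, so it does not settle which applies.

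**5. Season**
- Shifted by 52 weeks, the pre-study window (weeks −26 to 0) covers weeks 26 to 52. Follow-up covers weeks 16 to 40. They share weeks 26 to 40: 14 of 24 follow-up weeks, or 58%. The mismatch is partial.

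**6. Selection at entry**
- Section 4.1 excludes nurses who are on sick leave when recruited. A spell still running at recruitment therefore cannot contribute to the pre-study count, while a comparable spell can occur in follow-up. This pushes the change upward, against the direction of step 2, by an amount that the protocol does not allow one to calculate.

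**7. The controlled comparison**
- Over weeks 0-8 both arms have equal eight-week windows and only group 1 has the programme. Window length, season and entry selection apply equally to both.

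**The case against.** The protocol does not oversell this analysis. Section 5.3 calls it exploratory and says openly that it is within-group. None of hypotheses A to C in section 3.3 concerns absence, and the Synopsis analysis list promises only that sickness days will be quantified and reported. Whether to use a rate or an offset is often left to a statistical analysis plan, which may exist. All of this stands, and it lowers the severity. It does not remove the mismatch between a causal objective and a fixed analysis that cannot address it.

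The alternative has limits too. In weeks 0-8 group 1 is still attending sessions, so the contrast says nothing about absence after completion, the period that section 5.3 targets. The trial is open-label, absence is self-reported, 30% dropout is expected, and eight weeks of absence will give a wide interval. These limits are real. The contrast is still free of the before-after problems.

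A reader might go further and infer three things that the documents do not support:
- That the windows fall in different seasons. There are no calendar dates, and more than half of the follow-up weeks share calendar weeks with the earlier window.
- That the sick-leave exclusion cuts the pre-study window short. A nurse who was off earlier and has returned is eligible with all days counted. The exclusion is selection on status at recruitment.
- That the planned test is biased towards showing a benefit. The 8% depends on one reading of the window, and the selection effect works the other way.

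**Conclusion.** The concern holds in this form: the protocol asks whether the intervention reduces sickness absence and plans only a pooled, uncontrolled before-after comparison, while self-reported absence from the randomised weeks 0-8 is left unused. The missing control is the main defect. The net direction of bias cannot be determined from the document.

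The window mismatch is a second, smaller defect. It amounts to about 8% fewer raw days with no effect, on two assumptions: a constant absence rate, and counting from week 16 to week 40. It is zero if the recall period is six calendar months, at the price of about two weeks' overlap with group 2's intervention. On any reading, the six months and the week numbers need to be reconciled.

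That absence is available at week 8 in both arms follows from reading sections 4.3 and 4.4 together; the wording of the item is not shown. Severity is minor to moderate, because the analysis is labelled exploratory.

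**What to change.** 1. Add a between-group comparison of self-reported absence days over weeks 0-8 as the analysis that addresses the objective. Adjust for days in the prior six months, use a method suited to skewed counts (for example a negative binomial model, giving a rate ratio), and report a 95% CI.
2. Have the week-8 item ask for days since week 0, so that the window is the same in both arms.
3. Keep the before-after comparison as descriptive. Express it as days per unit time over a stated recall window, and say that it does not estimate an intervention effect.
4. Reconcile the six-month follow-up with weeks 16 to 40, and state the recall period in the survey item.

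The cost is one model on data already planned and small wording changes to the protocol and survey, with no extra participants or assessments. The limits of the eight-week contrast (imprecise, open-label, self-reported, confined to the period when group 1 is attending sessions) should be stated with the result.
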